6.7. Treatment Compliance

Treatment compliance for each patient will be calculated as:

$$Treatment\ compliance\ (\%) = 100 \times \frac{Total\ number\ of\ injections\ administered}{Total\ number\ of\ injections\ prescribed}$$

- The total number of injections prescribed can be derived from the Interactive Web Response System (IWRs) study drug dispense dataset.

- The total number of injections administered will be derived using the response to the question “Was dose administered?” on the *Exposure as Collected* eCRF page.

A patient will be considered overall compliant with study treatment within each treatment period if he/she misses no more than 20% of the expected doses and does not miss 2 consecutive doses. In the case a patient missed more than 20% of the prescribed doses during the study because of the investigator temporarily interrupted the treatment, the patient will not be considered as noncompliant.

The patient compliance will be summarized by cohort.

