7.2. Method of Treatment Assignment

Patients who meet all criteria for enrollment will be assigned to double-blind treatment at Visit 1 based on the ending treatment regimen of the originating study (see [Table AMAH.3](#)). The interactive web-response system (IWRS) will be used to assign prefilled syringes containing investigational product to each patient. Investigational product will be dispensed according to the Schedule of Activities (Section 2). Site personnel will confirm that they have located the correct prefilled syringes by entering a confirmation number found on the prefilled syringes into the IWRS.

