7.2.1. Selection and Timing of Doses

Study visits at which the investigational product is administered are preferred, if possible, to occur on the same day of the week. In any case, the study visits should occur within the visit window specified on the Schedule of Activities (see Section 2). The actual time of all dose administrations will be recorded in the patient's electronic case report form (eCRF). Study drug will be administered by site personal at Visits 1-13. Starting with Visit 14 patients should self-administer study drug on the day of the visit, and then every 8 weeks thereafter, preferably on the same day of the week.

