10.3.2.4. Treatment Compliance

Treatment compliance with investigational product will be summarized for patients who enter Study AMAH by the cohorts described in Section 10.3.1. A patient will be considered as having missed the visit if he or she fails to attend for administration of investigational product within the required treatment window as defined in the Schedule of Activities (Section 2). Overall compliance with therapy is defined to be missing no more than 20% of the expected doses and not missing 2 consecutive doses.

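### The compliance percentage divides by injections dispensed, so a skipped visit can leave both counts and the result is biased upward

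*SAP*

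**What the plan says.** SAP 6.7 gives two measures of compliance.

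- **The percentage.** This is injections administered over injections prescribed. For the denominator: "The total number of injections prescribed can be derived from the Interactive Web Response System (IWRs) study drug dispense dataset". For the numerator: "The total number of injections administered will be derived using the response to the question" on the exposure eCRF page that asks whether the dose was given.
- **The classification.** A patient is overall compliant "if he/she misses no more than 20% of the expected doses and does not miss 2 consecutive doses". An exception covers patients who exceed the 20% limit because the investigator interrupted treatment, but it is worded on prescribed rather than expected doses.

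Protocol 10.3.2.4 has the same two limits: "Overall compliance with therapy is defined to be missing no more than 20% of the expected doses and not missing 2 consecutive doses". It adds that a patient has missed a visit if he or she "fails to attend for administration of investigational product within the required treatment window" set by the Schedule of Activities. The SAP does not carry that sentence over.

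Under protocol 7.2 the IWRS assigns the syringes, and supply follows the Schedule of Activities. Site staff dose at Visits 1-13. After that, under protocol 7.2.1: "Starting with Visit 14 patients should self-administer study drug on the day of the visit, and then every 8 weeks thereafter". Visits move to 16-week spacing after Visit 14, with a log for home doses (protocol 7.1).

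**The concern.** A compliance percentage should compare doses taken with doses due. Here the only named source for the denominator is a record of what was handed out. If a patient does not come, nothing need be handed out, and the missed dose is then neither administered nor prescribed. The doses most likely to be missed are those the measure cannot see, so the error runs toward 100%.

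Two gaps in definition sit alongside this. The section moves between *expected* and *prescribed* without defining the first, so a programmer may build the classification on the schedule or on the dispense data. And the protocol's missed-visit sentence gives no way to identify a missed dose when no visit is due.

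At stake is the accuracy of a reported summary. The SAP's exposure measure (6.12.1) does not compensate: it runs from first dose to last treatment-period visit and does not subtract missed doses.

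**Working it through.** The plan states no expected number of doses or compliance rate, so there is no figure to reproduce. The counts below come from the dosing rule in protocol 5.1.2 (every 8 weeks, Week 0 to Week 208) and the visit weeks in the Schedule of Activities.

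**Doses due**

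- Total: 208/8 + 1 = 27.
- Given at site, Weeks 0-96: 96/8 + 1 = 13.
- Self-administered, Weeks 104-208: 27 − 13 = 14.
- Self-administered on a visit day: Weeks 104, 120, 136, 152, 168, 184, 200 and 208 = 8.
- Self-administered with no visit: Weeks 112, 128, 144, 160, 176 and 192 = 6.

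**Doses supplied per visit**, if each visit covers the doses up to the next: one at each of Visits 1-13, two at each of Visits 14-19, one at each of Visits 20 and 21. Check: 13 + 6 × 2 + 2 = 27.

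**The 20% limit on 27 doses**: 5/27 = 18.5% passes and 6/27 = 22.2% fails.

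**Percentage under each denominator**, assuming no dispense record for a visit that did not happen:

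| Patient | Schedule denominator | Dispense denominator |
|---|---|---|
| Six non-consecutive site visits skipped (Weeks 8, 24, 40, 56, 72, 88) | 21/27 = 77.8% | 21/21 = 100% |
| Visit 15 skipped (Weeks 120 and 128 not supplied) | 25/27 = 92.6% | 25/25 = 100% |
| One supplied home dose not taken (Week 112) | 26/27 = 96.3% | 26/27 = 96.3% |

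The overstatement is 22.2, 7.4 and 0 percentage points. The third row shows the limit of the problem: a dose already in the patient's hands stays in the denominator.

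**Classification of the same patients.** If *expected* means scheduled, the first patient fails the 20% limit and the second fails the two-consecutive limit, while each has a reported percentage of 100%. If *expected* is read as *prescribed*, both pass with no recorded misses. The text does not settle which reading applies.

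**Units.** The ratio is in injections, but the eCRF question is about a dose. A 250 mg dose is two syringes. A 125 mg dose is one active plus one placebo syringe until unblinding and one syringe afterwards (protocol Table AMAH.3). The SAP does not say how a dose answer becomes an injection count. For a 125 mg patient, counting syringes also gives a dose before unblinding twice the weight of one after it.

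**The case against.** The best defence is that the mechanism is inferred. The SAP says the prescribed count *can be* derived from the IWRS, which is permissive, and neither document says how the system records a skipped, late or rescheduled visit. If a late visit makes up the supply, nothing disappears. The dispense data can also err the other way, for example with syringes supplied but unused after early discontinuation. This stands as a limit on certainty. It does not remove the point, because the dispense dataset is the only source named and nothing in the text prevents the loss.

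Three stronger readings are tempting, and the documents do not support them.

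- **That a fully adherent completer fails the protocol's rule**, with 6/27 = 22.2% of doses lacking attendance. Protocol 10.3.2.4 defines a missed *visit*, not a missed dose. Where no visit is scheduled, none can be missed. The sentence does not reach those six doses; it does not count them as failures. For the same reason it does not show the protocol and SAP classifying one patient in opposite ways.
- **That the 20% and two-consecutive classification is itself built on IWRS counts.** It is worded on expected doses, and the IWRS sentence concerns only injections prescribed. The defect shown is the missing definition.
- **That this percentage is the main evidence on whether late loss of response reflects missed dosing.** No planned efficacy analysis uses compliance, and all efficacy analyses are on the ITT population. Serum concentrations are scheduled at Visits 15, 17, 19 and 21, dosing deviations go in the eCRF, and important protocol deviations are summarized.

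It is also fair that the SAP does not depend on attendance for home doses, since it uses the eCRF dose question.

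**Conclusion.** The concern holds for the percentage. As written, SAP 6.7 points to a denominator that can lose doses not supplied because a visit was skipped, and this biases the reported figure upward. The examples show an overstatement of 7.4 points for one skipped 16-week visit and 22.2 points for six skipped site visits; the size in the study depends on how often visits are skipped, which the documents do not give. The result rests on two assumptions: the IWRS holds no dispense record for a visit that did not occur, and the missed supply is not made up later.

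For the classification, the finding is that *expected* is undefined and the interruption exception switches to *prescribed*, so the two measures can contradict each other for the same patient. For the protocol, the finding is that its missed-visit sentence is silent on six of the 14 self-administered doses. The consequence is confined to a descriptive compliance summary; no efficacy endpoint changes.

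**What to change.** Amend SAP 6.7 as follows.

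1. Define expected doses from the every-8-week schedule, from Visit 1 to Week 208 or treatment discontinuation, excluding doses that fall in a documented investigator interruption.
2. Use that one count as the denominator of the percentage and for both the 20% and the two-consecutive limits. This also removes the present inconsistency, in which the interruption exception addresses only the 20% limit.
3. Count doses rather than syringes in numerator and denominator.
4. State that missed home doses are identified from the eCRF dose question, supported by the home dosing log, so that the six doses without a visit are covered.

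The cost is SAP wording and programming. Reported compliance may be somewhat lower than under the dispense-based count.

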8.1. Discontinuation from Study Treatment

8.1.1. *Permanent Discontinuation from Study Treatment*

Patients for whom investigational product should be permanently discontinued, irrespective of the reason, should complete the Post-Treatment Follow-Up and then be permanently discontinued from the study. Section 8.2 provides the list of criteria for permanent discontinuation of patients from study treatment and the study.

Patients discontinuing from the investigational product prematurely for any reason should complete AE and other follow-up procedures per Section 2 (Schedule of Activities), Section 5.1.3 (Post-Treatment Follow-up Period), Section 9.2 (Adverse Events), and Section 9.4 (Safety) of this protocol.

8.1.2. *Temporary Interruption (Withholding) of Study Treatment*

Some possible reasons for temporarily withholding investigational product include, but are not limited to, the following:

- Development of:
 - Serious or opportunistic infections, as described in Section 9.2.3).
 - Hypertension (see Section 9.4.2.1).
 - Latent tuberculosis (TB) infection (LTBI) (see Section 9.4.5.2).
 - Positive hepatitis B virus (HBV) deoxyribonucleic acid (DNA) results that are below the level of quantification (see Section 9.4.5.3).
 - Hepatic event or liver test abnormality: Investigational product should be withheld and additional testing performed following consultation with the Lilly-designated medical monitor, if the results of repeat tests following elevated alanine aminotransferase (ALT), alkaline phosphatase (ALP) or total bilirubin level (TBL) include one of the following (Section 9.4.6.1):
 - $ALT \geq 3 \times$ upper limit of normal (ULN) and $TBL < 2 \times ULN$
 - $ALP \geq 2 \times ULN$ and $TBL < 2 \times ULN$
 - $TBL \geq 2 \times ULN$ without increase from baseline in ALT/aspartate aminotransferase (AST)/ALP.
- Surgery: Patients requiring surgery at any time during the study should interrupt administration of the investigational product, beginning 8 weeks before the surgery or as early as possible within 8 weeks of surgery, and resume administration of the investigational product only after complete wound healing.

Cases that may merit temporary withholding of the study treatment should be discussed with the medical monitor. The medical monitor, in consultation with the investigator, will determine when it is appropriate to recommence study treatment.

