Treatment Period: All patients participating in Study AMAH will receive mirikizumab Q8W SC. The dose used in Study AMAH will depend on the treatment patients were receiving during the qualifying period of the originator study. For all treatment groups in Study AMAH, dosing begins at Visit 1 (Week 0) and continues to Visit 21 (Week 208).

- Patients entering from Study AMAJ or Study AMAK who received mirikizumab during the qualifying period, will continue to receive the dose they were receiving (either 250 mg mirikizumab Q8W SC or 125 mg mirikizumab Q8W SC). Patients entering from Study AMAJ or Study AMAK who were receiving secukinumab or placebo, respectively, during the qualifying period will receive 250 mg mirikizumab Q8W SC.
- Patients entering from Study AMBK will receive 250 mg mirikizumab Q8W SC.
- Patients entering from Study AMAF whose last treatment was 300 mg mirikizumab Q8W, on either the fixed dosing regimen or in the as needed (PRN) regimen, will start 250 mg mirikizumab Q8W SC in Study AMAH. Patients entering from Study AMAF whose last treatment was either 30 mg or 100 mg mirikizumab on a PRN regimen will start 125 mg mirikizumab Q8W SC in Study AMAH.
- After Study AMAH dosing is no longer blinded, patients who in the opinion of the investigator have experienced significant clinically meaningful loss of efficacy during study participation may be increased from 125 mg mirikizumab Q8W to 250 mg mirikizumab Q8W if it is determined by the patient and the investigator that the patient

might benefit from additional study drug in order to achieve satisfactory disease control. All patients who increase dosing to 250 mg mirikizumab Q8W will remain on this dose until completion of the study or early discontinuation.

Post-Treatment Follow-Up Period (12 Weeks): All patients, whether they discontinue early for any reason or complete study treatment, will enter the 12-week Post-Treatment Follow-Up period (Visit 801 and Visit 802) of Study AMAH.

For patients who have entered the Post-Treatment Follow-Up Period, psoriasis therapy with another agent(s), as determined appropriate by the investigator, is allowed.

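### The SAP's compliance exemption for investigator-ordered interruption starts only above 20% missed doses, so on the full schedule a run of 2 to 5 consecutive withheld doses is classed noncompliant with no relief

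*SAP*

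**What the plan says.** SAP 6.7 (Treatment Compliance) sets two conditions, both required. A patient is compliant if he or she "misses no more than 20% of the expected doses and does not miss 2 consecutive doses". One exemption follows: "In the case a patient missed more than 20% of the prescribed doses during the study because of the investigator temporarily interrupted the treatment", then "the patient will not be considered as noncompliant". The same section computes a compliance percentage as injections administered over injections prescribed, and says the prescribed number can be taken from the IWRS dispensing data. Results are summarized by cohort.

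Protocol 10.3.2.4 has the same two conditions and no exemption: "Overall compliance with therapy is defined to be missing no more than 20% of the expected doses and not missing 2 consecutive doses".

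Protocol 8.1.2 lists reasons for withholding study drug temporarily: certain infections, hypertension, latent tuberculosis, unquantifiable HBV DNA, liver test abnormalities and surgery. For surgery it says "Patients requiring surgery at any time during the study should interrupt administration of the investigational product, beginning 8 weeks before the surgery", or as soon as feasible inside that window, with dosing resumed once the wound has fully healed. The medical monitor, consulting the investigator, decides when dosing restarts.

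**The concern.** The compliance rule can fail in two ways, and the exemption answers only one of them. A patient whose dosing is withheld as the protocol directs, and who loses two or more doses in a row but no more than 20% overall, fails the consecutive-dose condition and has nothing to fall back on. Read literally, a patient withheld for longer passes the 20% mark and is excused altogether.

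At stake is the meaning of the reported compliance rate. Some patients who followed the protocol would be counted as noncompliant, and others with longer interruptions for the same reason would not. The sentence also leaves room for two programmers to implement it differently.

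**Working it through.** The documents give no figure to reproduce here. The check applies the stated rule to runs of withheld doses.

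**Inputs**
- Interval: "All patients participating in Study AMAH will receive mirikizumab Q8W SC", that is, every 8 weeks (SAP 5.1).
- Duration: Week 0 to Week 208 (SAP 5.1).
- Conditions and exemption: SAP 6.7, as quoted above.

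**Step 1: number of doses.** 208/8 + 1 = 27. If Week 208 is not counted, 26.

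**Step 2: where the exemption starts.** 0.20 × 27 = 5.4, so more than 20% means at least 6 missed doses. With 26 doses, 0.20 × 26 = 5.2, which again means at least 6.

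**Step 3: classify a run of m consecutive investigator-withheld doses out of 27.** The narrow reading takes the exemption to waive only the 20% condition.

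| m | Missed | Weeks between injections, 8(m+1) | Protocol 10.3.2.4 | SAP 6.7, literal | SAP 6.7, narrow |
|---|---|---|---|---|---|
| 1 | 3.7% | 16 | compliant | compliant | compliant |
| 2 | 7.4% | 24 | noncompliant | noncompliant | noncompliant |
| 3 | 11.1% | 32 | noncompliant | noncompliant | noncompliant |
| 4 | 14.8% | 40 | noncompliant | noncompliant | noncompliant |
| 5 | 18.5% | 48 | noncompliant | noncompliant | noncompliant |
| 6 | 22.2% | 56 | noncompliant | not noncompliant | noncompliant |
| 7 | 25.9% | 64 | noncompliant | not noncompliant | noncompliant |
| 8 | 29.6% | 72 | noncompliant | not noncompliant | noncompliant |

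The rows for 2 to 5 are noncompliant on every reading. Only the rows from 6 upward depend on how the exemption is read.

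**Step 4: fewer expected doses.** With n expected doses the exemption starts at floor(n/5) + 1. On the literal reading the unrelieved band is therefore 2 to floor(n/5):
- n = 25 to 27: 2 to 5 doses
- n = 20 to 24: 2 to 4
- n = 15 to 19: 2 to 3
- n = 10 to 14: 2 only
- n = 9 or fewer: empty

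**Step 5: can a protocol-directed hold cost two doses?** This is an illustration only. Take the surgery rule with three assumptions: the full 8 weeks before surgery are used, healing takes H weeks, and the surgery date is random relative to dosing. The off-drug window is 8 + H weeks, and for H up to 8 the chance that it contains two scheduled doses is H/8. That is 2/8 = 25%, 4/8 = 50% and 8/8 = 100% for H = 2, 4 and 8. The documents give no healing time, and the rule allows a hold that starts later, so these are not estimates of frequency.

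**Step 6: check of the fix.** If withheld doses are left out of both conditions, every run of 1 to 8 out of 27 is compliant and the discontinuity at 6 is gone.

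**The case against.** **The exemption may waive only the 20% condition.** Its trigger repeats only that condition, so this reading is possible. A run of 6 or more would then still fail on consecutive doses, and there would be no reversal. The wording of the consequence carries no such limit, which favours the literal reading, but the reversal should not be presented as the only interpretation. The objection does not rescue the 2-to-5 band, and it leaves the exemption useful only for interruptions that are not consecutive.

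**A withheld dose may never be dispensed, so it may not count as prescribed or missed.** SAP 6.7 uses expected and prescribed doses without relating them. However, the exemption itself speaks of prescribed doses missed because the investigator interrupted treatment. It thus treats such doses as both prescribed and missed, and it would hardly be needed otherwise. What stands is that the SAP should say how withheld doses are counted.

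**Protocol 10.3.2.4 ties a missed visit to failing to attend for dosing.** A patient who attends and has the dose withheld has arguably missed nothing. That sentence defines a missed visit, not a missed dose, so it leaves the matter open.

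**A reader might infer that any short interruption makes a patient noncompliant.** The documents do not support that. One withheld dose is compliant, and two in a row already mean 24 weeks between injections. Some holds may cost one dose or none: Protocol 9.4.5.2 allows resumption to be considered after 4 weeks of latent tuberculosis treatment, and Protocol 9.4.5.3 calls for an immediate repeat HBV DNA test.

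**Conclusion.** The point holds, and it is minor. As written, SAP 6.7 gives no relief to patients with 2 to 5 consecutive doses withheld under Protocol 8.1.2 on a schedule of 25 to 27 expected doses. The band is narrower for shorter schedules and empty at 9 or fewer. That part does not depend on how the exemption is read. The reversal, in which 6 or more withheld doses are excused while 2 to 5 are not, rests on the literal wording.

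A reader might go further and infer that the cohort compliance rates are materially wrong or that trial conclusions are affected. The documents support neither. They do not say how many patients will have such interruptions. Compliance is a descriptive summary, efficacy and safety analyses use the ITT population (SAP 6.1.1), no per-protocol set is defined, and no hypotheses are tested (SAP 6.4).

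**What to change.** Replace the exemption sentence in SAP 6.7 with:

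> Doses withheld by the investigator or medical monitor under protocol 8.1.2 are not expected or prescribed doses; they count neither toward the 20% limit nor toward the 2-consecutive-dose condition, and are left out of the denominator of the compliance percentage.

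In the same edit, state whether two doses missed by the patient on either side of a withheld dose count as consecutive. Report by cohort the number of patients with withheld doses, so that the reader can see how much the rule matters. Note in the CSR that this differs from Protocol 10.3.2.4, which has no exemption.

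The cost is one SAP sentence and one table row. No clinical rule changes. Protocol 7.6 already requires dosing deviations to be recorded in the eCRF, but it does not say that the record shows who ordered a hold or why. That should be confirmed, although the present exemption needs the same information.
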